This will allow us to test the hypothesis that clarifying questions affect the clinical management plans (see Table 5).

| Primary Outcome | Outcome Measure |
|-----------------|---|
| Agreement | Whether or not the clinician had to interrupt the call to ask clarifying questions Inter-rater reliability: the degree of agreement between DORA and the clinician on their assessments of the individual symptoms and the management plan |

Table 5. Primary Outcome Measurement

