8.3.2 Sampling

8.3.2.1 Sample Size

An audit of historical data was conducted for both Imperial and Oxford sites to provide evidence for an estimate of the study's sample size (see Appendices 7 and 8, respectively). All types of pre-assessment appointments throughout October 2020 were audited. October 2020 was used to project capacity in May-July 2021 on the assumption that recovery from this wave of the Covid-19 pandemic would follow a similar trajectory to recovery from the first wave. At Imperial, three consultant-led one-stop clinics are expected to be in place in July to mitigate surgery backlog. Sample size calculations were based on estimates deriving from this audit. As outlined in Table 7, Imperial currently sees about 7 patients per week in their one-stop clinic and pre-assesses about another 64 per week, almost 90% of whom are listed for surgery. If 80% of the total patients seen are estimated to be eligible for the trial, approximately 230 patients could be recruited from this clinic over the course of the study period. At Oxford, about 60 new patients are seen for pre-assessment per week, with approximately another 20 phone assessments for second eye are also done, with 90% being listed for surgery. With an estimated 70% of patients consenting to participate, and an attrition rate of 15%, 591 patients are expected to be recruited over the course of 26 weeks. An *a priori* power calculation was conducted to determine the minimum sample size necessary to achieve a power greater than 0.8 for a 0.05 level of significance [21]. On the basis of a total population of 1014, a 95% confidence level, and a 3% margin of error, a sample size of 520 is required for statistical significance.

| is set at 2 days due to | Imperial | Imperial | | Oxford | Oxford |
|---|--|---|--|----------------|--------------------------------------|
| | One-stop (Projected 3 clinics per week from 1/2021) | Pre-assessment (excluding one-stop) | | Pre-assessment | Phone pre-assessment (2nd eye) |
| Current Numbers Asso | essed | | | | |
| Mean Patients assessed per clinic | 10 | 8 | | 12 | 4 |
| Clinics per week | 3 | 8 | | 5 | 5 |
| Mean Patients Assessed per week | 30 | 64 | | 60 | 20 |
| Eligibility Assumption: | S | | | | • |
| % proceeding to surgery | 80% | 90% | | 90% | 90% |
| % routine cases | 80% | 80% | | 80% | 80% |
| % eligible for trial | 80% | 80% | | 90% | 90% |
| % ineligible due to complicated surgery | 5% | 5% | | 5% | 5% |
| Screening | | | | | |

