| Compound daily eligibility rate | 49% | 55% | | 62% | 62% |

Table 7. Indicative recruitment targets with assumptions of dropout at each stage. Screening capacity is set at 2 days due to staffing constraints.

| Number of days screening | 2 | 2 | | 2 | 2 |
|--|-----|-----|-----|-----|-----|
| Patients screened per week | 10 | 9 | | 15 | 5 |
| Estimated recruitmen | t | | | | |
| % consenting to trial | 70% | 70% | | 70% | 70% |
| Estimated average recruited per week | 7 | 6 | | 10 | 3 |
| Duration of trial (weeks) | 26 | 26 | | 26 | 26 |
| Estimated % of patients dropping out | 15% | 15% | | 15% | 15% |
| Estimated recruitment over trial | 150 | 135 | | 229 | 76 |
| Site Total | 286 | | 305 | | |
| Total | 591 | | | | |

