8.5 Data Analysis

8.5.1 Statistical Methods for Primary Outcome

The primary analysis will be the calculation of a kappa statistic of inter-observer (**DORA** & clinician) reliability of the decision made. Additionally, the outcome of the assessment will be compared with the 'real' complication rate determined by hospital medical records. This will be established by identification of any hospital presentation within 90-days after the last call. Given the specialist nature of ophthalmology services it can be assumed that patients will present through the eye casualty or clinic services offered by each site. Patients who present to the hospital eye service will be analysed on a case-by-case basis to ensure that complications that were missed by **DORA's** original assessment and complications that developed later can be differentiated. This analysis will provide baseline sensitivity and specificity data for use in preparing subsequent evaluations of efficacy.

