8.7 Generalisability

Limitations to the generalisability of the study results were noted in the previous section. However, it is expected that the results will be generalisable to the majority of cataract surgery patients. The vast majority of cataract surgeries are uncomplicated; only approximately 2.5% of cataract surgeries have intraoperative complications (which would have resulted in exclusion from this study) [3]. Therefore, if the results of this study are positive, they will demonstrate **DORA's** potential to manage almost all cataract surgery follow-up assessments.

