9.8 Stopping Guidelines

The study monitoring group will review the interim data for consideration of stopping the study early. Given that the estimated sample size is close to the minimum required for adequate power, the study will not be stopped early on the basis of efficacy or benefit. If the monitoring committee identifies any risks that have not been foreseen and mitigated against, the study will be paused while those risks are assessed.

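### The minimum of 520 is labelled a power calculation but is a ±3% margin of error for one proportion; the stated power has no calculation behind it

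*Protocol*

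**What the plan says.** Protocol 8.3.2.1 states that an a priori calculation was made "to determine the minimum sample size necessary to achieve a power greater than 0.8 for a 0.05 level of significance". The next sentence gives the result: "On the basis of a total population of 1014, a 95% confidence level, and a 3% margin of error, a sample size of 520", and adds that this number is needed for statistical significance. It names no hypothesis, effect size, test or target kappa.

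The planned size comes from elsewhere in the same section: "591 patients are expected to be recruited over the course of 26 weeks". That figure is the total of Table 7, which multiplies clinic volumes by eligibility, consent and dropout rates.

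Section 8.5.1 defines the main analysis: "The primary analysis will be the calculation of a kappa statistic of inter-observer" reliability. The SAP's primary outcome adds accuracy, sensitivity and specificity, for the overall decision and for each of five symptoms. Table 5 also counts as primary: "Whether or not the clinician had to interrupt the call to ask clarifying questions". Neither 8.5.1 nor the SAP gives a null or target value, or plans confidence intervals.

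Section 9.8 rules out stopping early for efficacy or benefit and gives this reason: "Given that the estimated sample size is close to the minimum required for adequate power". Section 8.7 says of the target population that "it is expected that the results will be generalisable to the majority of cataract surgery patients".

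**The concern.** Power belongs to a test of a stated null value against a stated alternative. A margin of error belongs to an interval estimate. The protocol announces the first and supplies the second. A reader, including an ethics committee or the monitoring group, would believe that 520 patients secure power above 0.8 for the agreement analysis. Section 9.8 builds a governance rationale on that belief.

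Two further points follow. A finite population correction is appropriate when the aim is to describe one closed list of patients, but 8.7 aims well beyond the patients screened during recruitment. And a margin for a proportion does not carry over to kappa or sensitivity, on which the preliminary safety evidence largely rests.

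**Working it through.** **1. Reproducing 520.** Inputs from 8.3.2.1: N = 1014, 95% confidence (z = 1.96), margin e = 0.03. The proportion p is not printed; 0.5, the usual worst case, is assumed.

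- n0 = z²p(1−p)/e² = 1.96² × 0.25 / 0.03² = 1067.1
- n = n0 / (1 + (n0 − 1)/N) = 1067.1 / (1 + 1066.1/1014) = 520.2

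This matches 520. With p = 0.6 the result is 1024.4 / (1 + 1023.4/1014) = 509.8. Adding an 80% power term to the same formula, (1.96 + 0.84)² × 0.25 / 0.03², gives about 2180, or 692 after the correction. So no power term was used.

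**2. Where 1014 probably comes from.** The source is not stated. Table 7 has "Patients screened per week | 10 | 9 | | 15 | 5". The sum is 39 per week, and 39 × 26 weeks = 1014. Unrounded, the four streams are 9.73 + 8.76 + 14.77 + 4.92 = 38.18 per week, or 992.7 over 26 weeks, which would give 515. The planned 591 is the same throughput after consent and dropout: 992.7 × 0.70 × 0.85 = 590.7. It is a recruitment projection and is not derived from 520.

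**3. Precision of a proportion without the correction.** The half-width is 1.96 × √(p(1−p)/n).

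- At p = 0.5: 4.3 points for n = 520 and 4.0 points for n = 591. A half-width of 3 points needs 1,068 patients.
- Solving for a half-width of 3 points: p = 0.858 or more at n = 520, and p = 0.834 or more at n = 591.

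**4. Precision of kappa and sensitivity at n = 591.** The documents give no flagged rate, sensitivity or specificity, so every value here is an assumption. The clinician's decision is the reference, as in 8.2.5.1. Let π be the proportion the clinician flags and q = π·sens + (1−π)(1−spec) the proportion DORA flags. Then observed agreement is π·sens + (1−π)·spec, chance agreement is πq + (1−π)(1−q), and kappa = (observed − chance)/(1 − chance).

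Example with π = 0.05, sensitivity 0.90, specificity 0.95: observed 0.9475, q = 0.0925, chance 0.8667, kappa = 0.0808/0.1333 = 0.61. Half-widths are 1.96 × the standard deviation of kappa over 60,000 simulated samples of 591. Sensitivity intervals are exact (Clopper-Pearson). Specificity is 0.95 throughout.

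| Flagged | Assumed sensitivity | Kappa | Kappa 95% half-width | Correct/flagged | 95% interval for sensitivity |
|---|---|---|---|---|---|
| 2% | 0.90 | 0.40 | 0.17 | 11/12 | 61.5–99.8% |
| 5% | 0.90 | 0.61 | 0.13 | 27/30 | 73.5–97.9% |
| 10% | 0.90 | 0.74 | 0.09 | 53/59 | 79.2–96.2% |
| 20% | 0.90 | 0.82 | 0.06 | 106/118 | 82.9–94.6% |
| 2% | 0.70 | 0.32 | 0.17 | 8/12 | 34.9–90.1% |
| 5% | 0.70 | 0.50 | 0.14 | 21/30 | 50.6–85.3% |
| 10% | 0.70 | 0.61 | 0.11 | 41/59 | 56.1–80.8% |
| 20% | 0.70 | 0.68 | 0.08 | 83/118 | 61.2–78.4% |

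The same 591 patients thus give a kappa half-width anywhere from 0.06 to 0.17, and a margin for a proportion cannot show which applies. The table covers the two-category management plan only, not the five four-category symptom kappas.

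**The case against.** Four objections deserve weight.

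- **Nothing depends on 520.** The planned size is 591, the stated aim is preliminary safety evidence, and the SAP contains no test or success threshold tied to 520. Section 8.2.5.1 does speak of testing whether clarifying questions alter management plans, but it names no test or effect size and the sample size is not linked to it. This stands, and it limits how serious the point is.
- **Some precision is stated.** A 3% margin is a precision statement, and accuracy is a primary SAP measure. If agreement is high, the margin holds without any correction (step 3). This also stands. The gap concerns kappa and sensitivity.
- **The reconstruction is partly inferred.** The value p = 0.5 and the origin of 1014 are not printed, the text cited for the method is not available here, and 9.8 does not name 520. The mislabelling does not depend on these inferences: the three stated inputs contain no effect size or power.
- **Flagged rates may be higher than those shown.** Appendix 6 reports that 7 of 25 Imperial patients (7/25 = 28%; the appendix prints 21%) had a complication requiring a management change at follow-up. That is not a rate of flags made from a telephone call. At 28% flagged, the kappa half-widths fall to about 0.05 (sensitivity 0.90) and 0.07 (0.70).

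A reader might also infer from the audits in Appendices 6 and 7 that recruitment will fall short of 520. The documents do not support this: 8.3.3.1 keeps screening open until the target is met, and 8.1.1 allows calls over six to twelve months so that targets can be reached.

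**Conclusion.** The point holds as a mislabelled justification that should be corrected. It is not a calculation error. The power claimed in 8.3.2.1 and repeated in 9.8 is undefined, because no null or alternative exists from which to compute it. The finite population correction conflicts with 8.7 and, at p = 0.5, makes a margin of ±4.3 points appear as ±3.

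A reader might infer that the study is underpowered, or that it needs 1,068 patients. Neither follows. The figure of 1,068 applies only to ±3 points at p = 0.5, whereas raw agreement in the table's scenarios is 90% to 95%. Whether 591 is enough for kappa or sensitivity depends on flagged rates and accuracy values that the documents do not give. The precision figures for kappa and sensitivity rest on the assumptions in step 4.

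**What to change.** - **(a) Protocol 8.3.2.1.** Delete the power and significance wording, the population of 1014 and the correction. Describe 591 as the recruitment projected in Table 7. State that it estimates a proportion, such as accuracy or the need for clarifying questions, to within at most ±4.0 points, and to about ±3 points or better if agreement is 83% or more.
- **(b) Same section.** Add the table in step 4 as illustrative precision for the management-plan kappa and for sensitivity. Label every input as an assumption, keep the unfavourable rows (2% flagged, sensitivity 0.70), and say that the four-category symptom kappas are not covered.
- **(c) Protocol 9.8.** Keep the rule against stopping early for efficacy or benefit, and remove the power rationale.
- **(d) SAP.** Add 95% confidence intervals for kappa (overall decision and each symptom), accuracy, sensitivity and specificity.

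The cost is rewording two protocol sections, adding one short table and one SAP line; no extra patients or data are needed. The downside is that the protocol loses its formal minimum and states a less favourable precision.

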8.3.2.2 Sampling Technique

All patients who are willing and eligible will be included in the sample receiving the **DORA** call. Of this sample, a subset will be selected to participate in a semi-structured interview to collect qualitative data about patients' perceptions of **DORA** (see 13.5 Appendix 5).

To select this subset, a stratified random sampling technique will be used. Patients will be divided based on demographic characteristics (gender, age, socio-economic status, and ethnicity) and clinical location (Oxford or Imperial). From these subgroups, patients will be randomly selected so that the sample interviewed is representative of the UK population. For example, we will randomly select to ensure the subset of patients being interviewed is split equally by gender and clinical location.

8.3.3 Recruitment

8.3.3.1 Participant Identification

Recruitment will take place in the pre-assessment sites and post-operative discharge lounges at the Imperial College Healthcare and Oxford University Hospitals NHS Trusts that conduct cataract surgeries. Participants will be made aware of the study via leaflets and discussion with healthcare providers during their pre-assessment and, if they are eligible, will be invited to participate. Patients

in the discharge lounges who have undergone uncomplicated cataract surgery will also be invited to participate in the study. Screening will continue at both sites until the target enrolment is achieved.

8.3.3.2 Consent

Study information will be shared with cataract surgery patients at their initial visit (and via post or telephone call for patients who are delayed by Covid-19 or cannot visit in person). Informed consent will be obtained in written form or verbally at the time of pre-assessment, surgical listing (in-person or virtually depending on the current Covid-19 guidelines), or in the discharge lounge following surgery (see 13.2 Appendix 2). Patients who have consented to participate will be given further information while they are in the discharge lounge to remind them about the call from **DORA**. This work will be performed by a dedicated research nurse at each site.

8.3.4 Adherence

The **DORA** calls will be recorded and the study team will monitor the use of the technology and assure the system is being used within designed parameters during the study.

8.4 Data Collection

8.4.1 Randomisation

8.4.1.1 Sequence Generation

Demographic data will be collected from all patients in the surveys that will be distributed to assess **DORA's** usability after patients have completed the call (see 13.4 Appendix 4). A computer random number generator will then be used to randomly select patients for semi-structured interviews from within each demographic subset collected at post-call surveys.

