7.5 Aims and Objectives

The purpose of this clinical investigation is to evaluate the safety, usability, acceptability, efficacy, and cost-effectiveness of Ufonia's autonomous cataract follow-up call system (**DORA**) at detecting patients that require further assessment. The aim is to establish preliminary safety evidence by examining the level of agreement between **DORA** and the supervising clinician on symptom and overall management plan decisions. Therefore, the focus will be on patients undergoing routine surgery. In order to achieve these aims, there are several objectives (see Figure 3):

- 1. To evaluate the level of agreement between **DORA** and an expert human clinician and identify any factors that affect that level of agreement;
- 2. To establish baseline rates of sensitivity and specificity for **DORA's** detection of patients that have postoperative complications;
- 3. To evaluate **DORA's** feasibility; i.e. whether **DORA** can engage with patients enough to produce sufficient data to perform an accurate assessment;
- 4. To evaluate the usability of an autonomous call, in comparison with existing standards of care, explore patient perceptions about whether DORA is acceptable, appropriate, satisfactory and evaluate cost-effectiveness of autonomous calls in comparison with existing standards of care.

Figure 3. Logic diagram of the study

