8.4.3 Methods of Data Collection

8.4.3.1 Quantitative data collection

The key data to be collected are **DORA** and the clinician's decisions. This will include data on symptoms as well as an overall assessment. Both **DORA** and the clinician will separately record their decisions about symptoms, clinical assessment, and management plan. **DORA** will record the decisions in the **DORA** database, which will be accessed by the study team during the evaluation to compare against the clinician decisions. Usability of the system will be assessed using the SUS and

TUQ questionnaires (see 13.4 Appendix 4). These will be delivered to all participants shortly after they have had the call with **DORA** via an online or paper survey (see Figure 6).

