 - e. £40.000 up to £50.000 per year
 - f. £50.000 up to £60.000 per year
 - g. £60.000 up to £70.000 per year
 - h. £70.000 up to £80.000 per year
 - i. Over £80.000 per year
 - j. Prefer not to say
- 7. EDUCATION: What is the highest educational or vocational qualification that you have or that you will receive if you complete your next set of exams?
 - a. No qualifications
 - b. 5 or more GCSE grades A-C
 - c. 4 or less GCSE grade A-C
 - d. GCSE grade D-G
 - e. 5 or more Scottish Standard Grades, grades 1-3
 - f. 4 or less Scottish Standard Grades, grades 1-3
 - g. 5 or more O Grades, grades 1-3 (Scottish Ordinary Grades)
 - h. 4 or less O Grades, grades 1-3 (Scottish Ordinary Grades)
 - i. Scottish Standard Grades, grades 4-7
 - j. Scottish Highers (either SCE or SQC)
 - k. Scottish Certificate Sixth Year Studies
 - I. SVQ level 1 or 2 (Scottish Vocational Qualifications)
 - m. SVQ level 3 (")
 - n. SVQ level 4 (")
 - o. SVQ level 5 (")
 - p. CSEs
 - q. 5 or more O levels
 - r. 4 or less O levels
 - s. GCE A levels or equivalent
 - t. NVQ level 1 or 2
 - u. NVQ level 3 or 4
 - v. NVQ level 5
 - w. GNVQ Foundation
 - x. GNVQ Intermediate
 - y. GNVQ Advanced
 - z. Certificate or Diploma of Higher Education
 - aa. HND (Higher National Diploma)
 - bb. Bachelor's degree
 - cc. Graduate Certificates and Diploma
 - dd. Post-degree professional qualification (eg banking accountancy, architecture, etc.)
 - ee. Master's Degree

- ff. Doctoral Degree
- gg. Don't know
- 8. EMPLOYMENT: Which of these descriptions best describes your current situation?
 - a. Working Full time (30 hours a week or more)
 - b. Working Part time (8-29 hours a week)
 - i. If (a) or (b): Apart from working, do you also study? (yes / no / DK)
 - c. Retired
 - d. Unemployed
 - e. Permanently sick or disabled
 - f. In community or military service
 - g. Undergraduate Student
 - h. Post graduate student
 - i. In full time education (not higher degree)
 - j. In part time education (not higher degree)
 - i. If (g)-(j): And apart from studying, do you also work? (yes / no / DK)
 - k. Doing housework, looking after children or other persons

System Usability Scale

Rated on a 5-point Likert scale, from 'Strongly Disagree' (1) to 'Strongly Agree' (5)

- 9. I think that I would like to use this system frequently.
- 10. I found the system unnecessarily complex.
- 11. I thought the system was easy to use.

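### Interviewees are drawn only from demographic groups formed by the post-call survey, so patients who return no survey cannot be selected

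*Protocol*

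**What the plan says.** Protocol section 8.3.2.2 starts from all willing and eligible patients who receive the DORA call. It takes a stratified random subset of them for interview, by gender, age, socio-economic status, ethnicity and site, "so that the sample interviewed is representative of the UK population".

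Section 8.4.1.1 says how this is done: "Demographic data will be collected from all patients in the surveys that will be distributed to assess" DORA's usability once the call is completed. A random number generator then selects interviewees "from within each demographic subset collected at post-call surveys". No other collection of demographics is stated, and nothing is said about a survey that is not returned.

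Section 8.4.3.1 describes distribution of the usability questionnaires, online or on paper: "These will be delivered to all participants shortly after they have had the call with" DORA. In Appendix 4 the income question can be answered "Prefer not to say".

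Table 6 lists interviews as the only measure of acceptability and of appropriateness. Objective 1 in section 7.5 includes a promise to "identify any factors that affect that level of agreement". Neither protocol section 8.5 nor the SAP names a factor, a demographic variable or a model for this.

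**The concern.** The two sections describe different sampling frames. Section 8.3.2.2 samples from everyone called. Section 8.4.1.1 can sample only from those who returned a survey, because the strata do not exist for anyone else.

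The survey has 37 numbered items, and the audited cohorts had mean ages of 71.5 (Imperial) and 76.36 (Oxford). No reminder procedure is stated, so complete return cannot be assumed.

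If patients who found DORA difficult return the survey less often, the interviews will under-represent them, and the acceptability findings will describe those who coped. The plan could not detect this. Section 8.6 compares interview findings with the quantitative usability data, but under section 8.4.1.1 both come from survey responders. Agreement between the two says nothing about non-responders.

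**Working it through.** **Planned size.** Table 7 gives 591, which reproduces. For each clinic type, recruitment = patients per clinic × 2 screening days × compound eligibility × 0.70 consent × 26 weeks × 0.85 retained. The last three factors multiply to 15.47.

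- Imperial one-stop: 10 × 2 × (0.80 × 0.80 × 0.80 × 0.95 = 0.486) × 15.47 = 150.5
- Imperial pre-assessment: 8 × 2 × (0.90 × 0.80 × 0.80 × 0.95 = 0.547) × 15.47 = 135.4
- Oxford pre-assessment: 12 × 2 × (0.90 × 0.80 × 0.90 × 0.95 = 0.616) × 15.47 = 228.6
- Oxford phone: 4 × 2 × 0.616 × 15.47 = 76.2
- Sum: 590.7, stated as 591

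**Patients outside the interview frame.** The documents give no survey response rate r, so r is an assumption. The number who cannot be selected is 591 × (1 − r).

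| Assumed response | Cannot be selected | Can be selected |
|---|---|---|
| 50% | 296 | 296 |
| 60% | 236 | 355 |
| 70% | 177 | 414 |
| 80% | 118 | 473 |
| 90% | 59 | 532 |

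At 50% each half is 295.5, rounded up.

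**What this does to a finding.** Suppose a view is held by a share p1 of responders and p0 of non-responders. A sample drawn only from responders is off by p1 − [r × p1 + (1 − r) × p0] = (1 − r) × (p1 − p0). That is half of the difference at 50% response and one tenth of it at 90%. The documents give neither the sign nor the size of p1 − p0.

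**What does not depend on the survey.** Kappa uses decisions that DORA and the clinician record during the call (sections 8.2.5.1 and 8.4.3.1). Site is known for everyone. Interruptions and reasons for clarifying questions are logged by the clinician (section 8.2.5.2).

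**Trigger for the survey.** Section 8.4.1.1 refers to patients who completed the call, section 8.4.3.1 to participants who had it. A call in which the clinician steps in may still be completed, since clarifying questions are a planned stage (section 8.2.3, Stage 3a). Whether a failed call leads to a survey therefore depends on which section is followed.

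**The case against.** The survey is meant for all patients, and the text excludes no other source of demographics. Figure 6, the data collection flow, is not shown, and the consent pages were not available. Patient details are entered before each call (section 8.2.3), and records are reviewed at both sites (section 8.2.4). The recruitment audits report age and first-eye status at both sites, and sex at Oxford. Age and sex are therefore probably recoverable, and any loss would fall mainly on ethnicity and socio-economic status. This stands as a reason why the fix is cheap. It does not rescue the plan, because the written selection rule uses the survey groups and has no fallback.

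Patients are also asked during the call for a recommendation score and the reason for it (section 8.2.5.2), and section 8.2.3 lists acceptability questions among the call elements. Some feedback therefore exists without the survey, although Table 6 counts the score under satisfaction only. Dissatisfied patients might even return surveys more often. The direction of bias is therefore open.

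Three stronger readings are tempting and not supported:

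- **Failed or interrupted calls drop out.** The two survey triggers differ, so this is not established. A call with no DORA decision would lack agreement data whatever the source of demographics.
- **Non-responders drop out of the objective 1 analysis.** No such analysis is specified, and its factors need not be demographic. Only a demographic analysis that relied on the survey would be limited to responders.
- **Most disagreements would lack covariates.** With disagreement rates q1 in responders and q0 in non-responders, the share without covariates is (1 − r)q0 / [r × q1 + (1 − r)q0]. With q1 = 5% and q0 = 15% it is 0.06/0.09 = 67% at 60% response and 0.03/0.07 = 43% at 80%. With equal rates at 60% response it is 40%. All these rates are assumed, so the result only returns what was put in.

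**Conclusion.** The point holds for the interview sample. As written, section 8.4.1.1 replaces the frame of all patients called with survey responders and so works against the representativeness that section 8.3.2.2 asks for. At an assumed response of 50% to 90%, about 296 to 59 of 591 patients could not be interviewed. It matters most for acceptability and appropriateness. A bias in DORA's favour is plausible, but nothing in the documents shows it.

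The primary kappa is untouched. For objective 1 the consequence is conditional: a demographic analysis of agreement, if one is done, would cover responders only unless covariates come from elsewhere. This is a low-severity improvement to the design, worth making because it costs little.

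**What to change.** 1. For every enrolled patient, take age, sex, ethnicity (where recorded) and first or second eye from the hospital record, and note site. Do this at consent or call set-up, before interview selection. The 90-day record review may come too late for that purpose.
2. Draw the stratified interview sample from all patients called, including those whose call was interrupted, on age, sex, ethnicity and site. Use survey-based socio-economic status only where available. Place unreturned surveys and declined income answers in an 'unknown' stratum that can still be selected.
3. Reconcile sections 8.4.1.1 and 8.4.3.1 on whether the survey goes to patients who completed the call or to all who had it.
4. Use the same record-based covariates for any demographic analysis of agreement under objective 1, so that it covers all calls with both a DORA and a clinician decision. Label it exploratory, because disagreements may be few.

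The cost is the extraction of a few fields from records the study already uses, and a check that the consent wording covers it. Socio-economic status will stay incomplete, and ethnicity may be missing for some patients.
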